**6.18.4. Planned Exploratory Health Outcomes/Quality-of-Life Analyses**

[Table RHBX.6.14](#) includes the description and derivation of the exploratory health outcomes and QOL measures.

[Table RHBX.6.15](#) provides the detailed analyses including analysis type, method and imputation, population, time point, and treatment group comparisons for the exploratory health outcomes and QOL analyses.

**Table RHBX.6.14. Description and Derivation of Exploratory Health Outcomes and Quality-of-Life Measures**

Measure	Description	Variable	Derivation / Comment	Missing Items
European Quality of Life – 5 Dimensions 5 Level (EQ-5D-5L)	EQ-5D-5L: is a standardized measure of health status used to provide a simple, generic measure of health for clinical and economic appraisal. The EQ-5D-5L consists of 2 components: a descriptive system of the respondent’s health and a rating of his/her current health state using a 0- to 100-mm VAS. The descriptive system comprises the following 5 dimensions: item 1: mobility item 2: self-care item 3: usual activities item 4: pain/discomfort item 5: anxiety/depression The respondent is asked to indicate his/her health state by ticking (or placing a cross) in the box associated with the most appropriate statement in each of the 5 dimensions.	EQ-5D mobility, EQ-5D self-care, EQ-5D usual activities, EQ-5D pain/ discomfort, EQ-5D anxiety/ depression	Five health profile dimensions, each dimension has 5 levels: 1 = no problems 2 = slight problems 3 = moderate problems 4 = severe problems 5 = extreme problems It should be noted that the numerals 1 to 5 have no arithmetic properties and should not be used as a primary score.	Each dimension is a single item, missing if missing.
		EQ-5D-5L UK Population-based index score	Uses the concatenation of the value of each EQ-5D-5L dimension score in the order: item1; item2; item3; item4; item5. Derive EQ-5D-5L UK Population-based index score according to the link by using the UK algorithm (Szende et al. 2007) to produce a patient-level index score between -0.59 and 1.0 (continuous variable): https://euroqol.org/eq-5d-instruments/eq-5d-5l-about/valuation-standard-value-sets/crosswalk-index-value-calculator/	If any of the items is missing, the index score is missing
	The VAS records the respondent’s self-rated health on a vertical VAS where the endpoints are labeled 100 = “best imaginable health state” and 0 = “worst imaginable health state”.	EQ-5D VAS	Range from 0 = “worst imaginable health state” to 100 = “best imaginable health state.” Note: higher value indicates better health state.	Single item, missing if missing

Measure	Description	Variable	Derivation / Comment	Missing Items
Healthcare Resource Utilization	Healthcare resource utilization data regarding the number of visits to medical care providers, such as general practitioners, specialists, physical, or occupational therapists, and other nonphysical care providers for services outside of the clinical trial; emergency room admissions; hospital admissions; and concomitant medications will be recorded by the investigator in the study's CRF.	Visits to medical care providers (except hospitals)	Derivation will be performed within each treatment period	NA
		Days in hospital		
		Number of hospital admissions (Medical ICU, surgical ICU, coronary ICU, general ward, trauma unit, unknown or other)		
		Healthcare providers (type of specialist for healthcare practitioner)		

Abbreviations: ICU = intensive care unit; NA = not applicable; UK = United Kingdom; VAS = visual analog scale.

**Table RHBX.6.15. Description of Exploratory Health Outcomes and Quality-of-Life Analyses**

Measure	Variable	Analysis Method (Sections 6.1 and 6.3)	Population (Section 6.1.1)	Comparison / Time Point
European Quality of Life – 5 Dimensions 5 Level (EQ-5D-5L)	EQ-5D mobility, EQ-5D self-care, EQ-5D usual activities, EQ-5D pain/discomfort, EQ-5D anxiety/depression	For each EQ-5D dimension, the proportion of patients with “no problems” will be analyzed by: Logistic regression analysis with NRI; Fisher’s exact test with NRI	ITT Population	IXE80Q2W & IXE80Q4W vs. placebo at Weeks 16 and 52
	Change from baseline in: EQ-5D-5L UK Population-based index score, EQ-5D VAS	ANCOVA with mBOCF	ITT Population	IXE80Q2W & IXE80Q4W vs. placebo at Weeks 16 and 52
Healthcare Resource Utilization	Visits to medical care provider; Days in Hospital; Number of hospital admissions; Healthcare provider	Descriptive statistics	ITT Population	Overall comparison in Period 2 by Kruskal Wallis test

Abbreviations: ANCOVA = analysis of covariance; EQ-5D-5L = European Quality of Life – 5 Dimensions 5 Level; ITT = intent-to-treat; IXE80Q2W = ixekizumab 80 mg every 2 weeks; IXE80Q4W = ixekizumab 80 mg every 4 weeks; mBOCF = modified baseline observation carried forward; NRI = nonresponder imputation; UK = United Kingdom; VAS = visual analog scale.

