Unless otherwise specified, treatment groups of ixekizumab 80 mg Q2W and Q4W will be analyzed without regard to starting dose.

The primary analysis method for treatment comparisons of categorical efficacy and health outcomes variables at specific time points will be made using a logistic regression analysis with treatment, geographic region (Europe and non-Europe), and screening MRI/CRP status in the model using PROC Logistic with a Wald test. The odds ratio and 95% CIs will be reported; treatment difference and 95% CI will also be reported. Secondary analysis will be conducted using a Fisher's exact test. In the case when logistic regression model does not produce statistical results due to sparse data, Fisher's exact test will be used.

As a secondary analysis for the primary and major secondary categorical efficacy measures, a categorical, pseudo-likelihood based mixed-effects model of repeated measures (categorical mixed-effects model of repeated measures [MMRM]) estimating the percentage of patients achieving response across postbaseline visits may be used. The model will include treatment, geographic region, screening MRI/CRP status, visit, and treatment-by-visit as fixed factors. The binomial distribution and the logit link will be used. The restricted maximum likelihood (REML) will be used. An unstructured covariance matrix will be used to model the within-patient variance-covariance errors. The Kenward-Roger approximation will be used to estimate the denominator degrees of freedom. The Newton-Raphson with ridging optimization technique will be used to aid with convergence. The probability of response, the corresponding 2-sided 95% CI, and the p-value for treatment comparisons at Week 16 (Visit 8), Week 52 (Visit 15), and all other postbaseline visits will be reported.

If the unstructured covariance matrix results in a lack of convergence, the heterogeneous Toeplitz covariance structure, followed by the heterogeneous autoregressive covariance structure, followed by the compound symmetry will be used. This order is specified according to a decreasing number of covariance parameters in the structure. The sandwich estimator (Diggle et al. 1994) for the covariance estimation will be used by specifying the EMPIRICAL option in SAS PROC MIXED. When sandwich estimation is used, the Kenward-Roger approximation for denominator degrees of freedom cannot be used. Instead, DDFM= BETWITHIN option will be used to estimate denominator degrees of freedom.

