### 6.3.1. Nonresponder Imputation

Analysis of categorical efficacy and health outcome variables will be assessed using a nonresponder imputation (NRI) method. Patients will be considered nonresponders for the NRI analysis if they do not meet the clinical response criteria or have missing clinical response data at the primary analysis time points. All nonresponders at Week 16 (Visit 8), as well as all patients who discontinue study treatment at any time prior to Week 16 for any reason, will be defined as nonresponders for the NRI analysis at Week 16. Similarly, all nonresponders at Week 52 (Visit 15), as well as patients who discontinue study treatment at any time prior to Week 52 for any reason, will be defined as nonresponders for the NRI analysis at Week 52. Patients who are deemed as inadequate responders by the investigator on or after Week 16 but remain on initially assigned blinded study treatment and only have modifications in concomitant medications will not influence whether or not a patient would be considered a nonresponder. Patients who stopped originally assigned blinded study treatment and use rescue ixekizumab 80 mg Q2W will be analyzed as nonresponders for the Week 52 analysis. They will be considered as nonresponders after the time of initiation of biologic rescue of ixekizumab 80 mg Q2W.

Randomized patients without at least 1 postbaseline observation will also be defined as nonresponders for the NRI analysis.

The NRI may be applied at any time point specified for analysis.

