		SPARCC enthesitis score = 0	SPARCC enthesitis score = 0 refers to complete resolution in enthesitis. Analysis of SPARCC enthesitis score = 0 only applies to patients with baseline enthesitis (SPARCC enthesitis >0).	Missing if observed value is missing
Tender Joint Count (TJC)	The number of tender and painful joints will be determined by examination of 46 joints (23 joints on each side of the patient’s body). The 46 joints are assessed and classified as tender or not tender.	TJC total score	Adjusted sum of the pain/tenderness for all 46 joints: $\left( \frac{\text{sum of all joints checked to be painful/tender}}{\text{number of evaluable joints}} \right) \times 46$ See Appendix 4 for details.	If more than half of the joint scores are non-evaluable, the total score will be missing.
		TJC change from baseline	Calculated as: observed TJC – baseline TJC only applies to patients whose baseline TJC >0.	Missing if baseline or observed value is missing
		Proportion of patients with TJC = 0 when baseline TJC > 0	Analysis of TJC = 0 only applies to patients whose baseline TJC > 0.	Missing if observed value is missing

Measure	Description	Variable	Derivation / Comment	Imputation Approach if with Missing Components
		Proportion of patients with TJC = 0 for patients with current or historical peripheral arthritis at baseline	Analysis of TJC = 0 only applies to patients with current or historical peripheral arthritis at baseline	Missing if observed value is missing
Swollen Joint Count (SJC)	The number of swollen joints will be determined by examination of 44 joints (22 joints on each side of the patient’s body). The 44 joints are assessed and classified as swollen or not swollen.	SJC total score	Adjusted sum of the pain/tenderness for all 44 joints. $\left( \frac{\text{sum of all joints checked to be swollen}}{\text{number of evaluable joints}} \right) \times 44$ See Appendix 4 for details.	If more than half of the joint scores are nonevaluable, the total score will be missing.
		SJC change from baseline	Calculated as: observed SJC – baseline SJC Only applies to patients whose baseline SJC >0.	Missing if baseline or observed value is missing
		Proportion of patients with SJC = 0 when baseline SJC > 0	Analysis of SJC = 0 only applies to patients whose baseline SJC > 0.	Missing if observed value is missing

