**Table RHBX.6.7. Description of Health Outcomes and Quality-of-Life Analyses**

Measure	Variable	Analysis Method (Sections 6.1 and 6.3)	Population (Section 6.1.1)	Comparison/Time Point	Analysis Type
36 item Short Form Health Survey (SF-36)	PCS (Major Secondary), change from baseline	MMRM	ITT Population	IXE80Q2W & IXE80Q4W vs. placebo at Weeks 16 and 52 and all other postbaseline visits in Period 2	Major secondary efficacy analysis is MMRM analysis for ITT Population comparing IXE80Q2W & IXE80Q4W vs. placebo at Weeks 16 and 52 (Section 6.10.2).
		ANCOVA with mBOCF	ITT Population	IXE80Q2W & IXE80Q4W vs. placebo at Weeks 16 and 52 and all other postbaseline visits in Period 2	Health Outcomes/QOL analyses (Section 6.11).
		Descriptive statistics	IR Population	Period 2 post initiation of biologic rescue of ixekizumab 80 mg Q2W	Health Outcomes/QOL analyses (Section 6.11).
	MCS, domain scores (for both transformed and norm-based scores), change from baseline	MMRM	ITT Population	IXE80Q2W & IXE80Q4W vs. placebo at Weeks 16 and 52 and all other postbaseline visits in Period 2	Health Outcomes/QOL analyses (Section 6.11).
		ANCOVA with mBOCF	ITT Population	IXE80Q2W & IXE80Q4W vs. placebo at Weeks 16 and 52 and all other postbaseline visits in Period 2	Health Outcomes/QOL analyses (Section 6.11).
	ASAS Health Index (ASAS HI)	ASAS HI change from baseline -	MMRM	ITT Population	IXE80Q2W & IXE80Q4W vs. placebo at Weeks 16, 52 and all other postbaseline visits in Period 2
ANCOVA with mBOCF			ITT Population	IXE80Q2W & IXE80Q4W vs. placebo at Weeks 16 and 52 and all other postbaseline visits in Period 2	Health Outcomes/QOL analyses (Section 6.11).
	Proportion of patients with $\geq 3$ points	Logistic regression with NRI;	ITT population With Baseline Score $\geq 3$	IXE80Q2W & IXE80Q4W vs. placebo at Week 16, 52 and all other	Health Outcomes/QOL analyses

Measure	Variable	Analysis Method (Sections 6.1 and 6.3)	Population (Section 6.1.1)	Comparison/Time Point	Analysis Type
	improvement from baseline	Fisher’s exact test with NRI		postbaseline visits in Period 2	(Section 6.11).
	Proportion of patients reaching Good ASAS HI (defined as ASAS HI ≤5)	Logistic regression with NRI; Fisher’s exact test with NRI	ITT population With Baseline Score >5	IXE80Q2W & IXE80Q4W vs. placebo at Week 16, 52 and all other postbaseline visits in Period 2	Health Outcomes/ QOL analyses (Section 6.11).

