## 6.18. Planned Exploratory Analyses

- To assess the psychometric properties (including reliability, validity, and responsiveness) of the ASAS HI in the ITT Population
- To assess the psychometric properties (including reliability, validity, and responsiveness) of the SF-36 components and norm-based domain scores in the ITT Population.
- To explore the impact of each ixekizumab regimen on change from baseline in measures of health utility (EQ-5D); and healthcare resource utilization in the double-blind dosing period in the ITT Population.

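### The EQ-5D 'no problems' tests ignore the baseline level: patients already at level 1 dilute an effect on resolution, and at Week 52 NRI can add a rescue difference unrelated to the dimension

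*SAP*

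**What the plan says.** SAP Section 6.18 sets the exploratory aim: "To explore the impact of each ixekizumab regimen on change from baseline in measures of health utility (EQ-5D"). Table RHBX.6.15 has two EQ-5D rows.

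- **Dimensions.** "For each EQ-5D dimension, the proportion of patients with “no problems” will be analyzed by: Logistic regression analysis with NRI", and also by Fisher's exact test with NRI. The population is ITT without restriction, and the comparison is "IXE80Q2W & IXE80Q4W vs. placebo at Weeks 16 and 52".
- **UK index and VAS.** Change from baseline by ANCOVA with mBOCF. Under Section 6.2 this model carries the baseline value.

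Table RHBX.6.14 defines the scale: "each dimension has 5 levels: 1 = no problems", rising to extreme problems at level 5. Section 6.1.2.1 gives the logistic model: "treatment, geographic region (Europe and non-Europe), and screening MRI/CRP status in the model using PROC Logistic with a Wald test". Section 6.2 adds a baseline value for MMRM and ANCOVA and does not mention logistic regression.

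Section 6.3.1 applies NRI to categorical health outcomes. It makes a nonresponder of anyone who stops study treatment before the visit or has missing data. Of patients given rescue ixekizumab it says: "They will be considered as nonresponders after the time of initiation of biologic rescue of ixekizumab 80 mg Q2W".

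Some comparable endpoints are limited to patients not already in the target state. For ASAS HI of 5 or less, Table RHBX.6.7 uses "ITT population With Baseline Score >5". For joint counts, Table RHBX.6.4 says "Analysis of TJC = 0 only applies to patients whose baseline TJC > 0". The main ASDAS <2.1 analysis in Table RHBX.6.5 requires a baseline ASDAS of at least 2.1.

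**The concern.** No inclusion criterion in Protocol Section 5.1 requires a problem on any EQ-5D dimension. Entry depends on axial disease, BASDAI, back pain and inflammation. Some patients may therefore start at level 1, for example on self-care or anxiety/depression. The plan mixes them with patients who have a problem to resolve, with two consequences.

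1. **Dilution.** A patient at level 1 at baseline cannot improve. While observed at level 1, that patient counts as a responder in either arm, and this shrinks a real difference in resolution. It is the main issue at Week 16.
2. **Rescue counted as loss of 'no problems'.** Rescue runs from Week 16 to Week 44 (Protocol Section 6.1) and follows the Week 16 assessments (heading of Protocol Section 6.8.2), so it acts on the Week 52 result. A level-1 patient rescued for spinal symptoms leaves the 'no problems' count on all five dimensions, whatever was answered. If placebo patients are rescued more often, each dimension on which some patients start at level 1 shifts in favour of ixekizumab. At Week 16 only discontinuation and missing data can do this.

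At stake is whether five p-values that look like effects on self-care, anxiety and so on can be read that way.

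**Working it through.** **Inputs from the documents.** n = 100 per arm, two-sided Fisher's exact test at 0.05, and ASAS40 rates of 46% v 18% (SAP Section 5.2). The documents give no EQ-5D rates.

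**Inputs assumed.** b, the share at level 1 at baseline on a dimension, is 20% to 80%. r, the rescue or discontinuation rate by Week 52, is 30% on ixekizumab and 30% to 50% on placebo.

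**Step 1: the plan's own figures.** Exact Fisher power for 46% v 18% is 98.8%, against the stated 98% or so. The Week 52 power table gives 100.0, 99.9, 93.5, 100.0, 97.4 and 66.9%, against 99, 99, 93, 99, 97 and 66%. The same function is used below.

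**Step 2: dilution, no rescue.** Suppose level-1 patients stay at level 1, and a share p of the others resolves. The all-ITT rate is b + (1−b)p, so the difference is (1−b)(p_ixe − p_pbo). For illustration only, borrow p = 46% v 18%, a 28-point difference.

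| b | All-ITT difference | Power, all ITT | Power, baseline level ≥2 (n per arm) |
|---|---|---|---|
| 20% | 28 × 0.8 = 22.4 points | 87.5% | 96.1% (80) |
| 40% | 28 × 0.6 = 16.8 points | 63.3% | 88.6% (60) |
| 60% | 28 × 0.4 = 11.2 points | 36.9% | 70.5% (40) |
| 80% | 28 × 0.2 = 5.6 points | 16.1% | 37.3% (20) |

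**Step 3: rescue at Week 52, no effect on the dimension.** Nobody changes level. The reported rate is b(1−r), so the difference is b(r_pbo − r_ixe).

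| b | Reported, r = 30% v 50% (ixe v pbo) | Fisher rejects | Reported, r = 30% v 40% | Fisher rejects |
|---|---|---|---|---|
| 30% | 21% v 15% | 15% | 21% v 18% | 6% |
| 50% | 35% v 25% | 29% | 35% v 30% | 9% |
| 70% | 49% v 35% | 47% | 49% v 42% | 14% |

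At equal rescue the rejection rate is 3–4%. There is then no between-arm bias, but both arms' levels are too low. At b = 50% and r = 30% v 50%, half of each arm is truly at level 1, yet 0.5 × 30 = 15 and 0.5 × 50 = 25 patients per 100 are moved out. Restricted to baseline level ≥2, this scenario gives 0% v 0%.

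**Step 4: does restriction always gain power?** Let a share m of level-1 patients keep level 1. The all-ITT rate becomes b·m + (1−b)p. Take m = 90% on ixekizumab v 80% on placebo, and p = 40% v 20%.

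- b = 50%: 0.5 × 0.9 + 0.5 × 0.4 = 65% v 0.5 × 0.8 + 0.5 × 0.2 = 50%. Power is 53% all-ITT v 52% restricted.
- b = 70%: 0.7 × 0.9 + 0.3 × 0.4 = 75% v 0.7 × 0.8 + 0.3 × 0.2 = 62%. Power is 45% all-ITT v 30% restricted.

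If ixekizumab also helps patients keep level 1, the gain in Step 2 can vanish or reverse.

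**The case against.** The strongest defence is that NRI defines a composite. Section 6.10.1 describes the ASAS40 analysis as the effect attributable to the originally randomized treatment. Read the same way, the dimension outcome is 'no problems without rescue or discontinuation', and a rescue difference is then a real difference between arms. This stands as far as it goes: the rejection rates in Step 3 are false positives only for a claim about the dimension itself. But the table's label names the dimension alone, and every dimension would carry the same rescue signal.

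Four stronger readings are tempting, and the documents do not support them.

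- *Rescued patients are recorded as having a problem they never had.* Section 6.3.1 calls them nonresponders and assigns no one to levels 2 to 5. Some may also have worsened before rescue; NRI discards the answer that would show it.
- *The change-from-baseline aim is unmet.* The next row of Table RHBX.6.15 serves it, with baseline in the model.
- *The SAP always restricts such endpoints.* It does not. Table RHBX.6.5 also tests joint counts and enthesitis scores of 0 in patients with current or historical disease. It tests ASDAS inactive disease in all ITT patients, and lists plain ITT for several ASDAS <2.1 rows.
- *Leaving out baseline biases the comparison.* Randomization balances baseline in expectation, so omission costs precision. The directional problem comes from NRI combined with unequal rescue.

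**Conclusion.** The point holds as a modest one. The EQ-5D dimension tests mix resolution, maintenance and freedom from rescue in a single proportion, and the label does not say so. The two formulae, (1−b) for dilution and b(r_pbo − r_ixe) for the added Week 52 difference, apply under the simple scenarios stated. Their size cannot be taken from the documents, because b and the rescue rates are assumptions. The Week 52 effect ranges from nothing at equal rescue to a 47% rejection rate at b = 70% with 50% v 30% rescue.

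The analysis is exploratory and outside the testing lists of Section 6.5, so the matter is one of interpretation. The change is worth making because it is cheap and follows the convention already used for ASAS HI.

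**What to change.** In Table RHBX.6.15:

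1. For each dimension, analyse 'no problems' with NRI in ITT patients at level 2 or worse on that dimension at baseline, and label it resolution.
2. For patients at level 1 at baseline, give a shift table of observed levels by arm and visit, without NRI, so that maintenance and worsening appear as the patient answered.
3. If an all-ITT comparison is kept, add baseline level (1 v ≥2) to the logistic model and label the outcome 'no problems without rescue or discontinuation'.

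The cost is SAP wording. EQ-5D-5L is already scheduled at Visit 2 (Protocol Appendix 2), and baseline level precedes treatment, so the restricted comparison remains randomized. There are two downsides. Fewer patients remain in dimensions where most start without a problem. The restricted test also misses an effect on keeping level 1, which only the shift table, or the all-ITT version if kept, would show.
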